#### **9.5.5 Physical Measurements**

All physical examination data will be listed by subject.

#### **9.5.6 Chest X-Ray Findings**

Descriptive statistics summaries of chest X-ray findings will be provided by scheduled visit using counts and percentages of subjects in each category (Normal, Abnormal NCS, Abnormal CS, Not Done).

All chest X-ray data will be listed by subject.

### **9.5.7 Antibody Formation**

Descriptive statistics summaries of anti-drug antibodies (ADA) will be provided by scheduled visit.

All ADA data will be listed by subject.

### **9.5.8 Exposure to Investigational Product**

Descriptive statistics summaries of study drug administration will include the number and percent of subjects receiving each study drug at each scheduled dosing. The total dose given (mg) and extent of exposure (days) will also be provided. Extent of exposure will be calculated as the date of last dose – the date of first dose + 1.

All study drug administration data will be listed by subject.

### **9.5.9 Exposure to Concomitant Medication**

Medications with an end date prior to the first dose of study drug will be identified as prior medications; medications with an end date on or after the first dose of study drug will be identified as concomitant medications. Similarly, procedures with a date prior to the first dose of study drug will be identified as prior procedures; procedures with a date on or after the first dose of study drug will be identified as concomitant procedures. Prior medications and prior procedures will be included in listings only.

Medications will be coded using WHODrug version Mar 2020 or later and will be reported by Anatomical Therapeutic Chemical (ATC) classification level 4 and Preferred Drug Name. Procedures will be coded using MedDRA version 23.0 or later to a SOC and PT.

Descriptive statistics summaries of the number and percent of subjects who receive each concomitant medication will be summarized. Similarly, descriptive statistics summaries of the number and percent of subjects who receive each concomitant procedure will also be summarized by SOC and PT.

Additionally, concomitant medications and procedures related to CF will be recorded separately. Listings of prior and concomitant medications and therapies will be provided by subject.

## **9.6 Efficacy Analyses**

All efficacy summaries outlined in this section will be created using the Safety Analysis Set.

### **9.6.1 Spirometry**

Spirometry will be evaluated in NHVs and CF patients. In general, spirometry for NHVs are considered a safety measurement and spirometry for CF patients are considered both a safety and efficacy measurement. For CF patient cohorts, use of an inhaled bronchodilator will be recorded at each spirometry assessment. All CF patient spirometry summaries will identify use of an inhaled bronchodilator as recorded on the Spirometry eCRF.

---

Descriptive statistics summaries of pulmonary function parameters obtained from the spirometry assessments will be provided by scheduled timepoint. Absolute changes and percentage changes from baseline will be included. In addition to an overall summary, subgroup analyses (as defined in Section 4.2) will be provided.

A sensitivity analysis of FEV1 and ppFEV1 will be performed for CF patient cohorts if use of an inhaled bronchodilator at any post-baseline assessment does not match use of an inhaled bronchodilator at the baseline assessment for any CF patients. The sensitivity analysis will consist of a summary of FEV1 and ppFEV1 values with absolute and percent changes from baseline by scheduled visit, excluding any post-baseline spirometry assessments where the bronchodilator status does not match the bronchodilator status at baseline. Subgroup analyses will not be provided for the sensitivity analysis.

Plots of mean (+/- SD) FEV1 (L) and ppFEV1 (%) over time will be provided by study day from baseline to the EOS visit. Plots for CF patient cohorts will additionally include a plot from baseline to Day 37 (Cohorts 2b-4b) and a plot from baseline to Day 43 (Cohort 6).

Additionally, a plot will be provided for CF patient cohorts to visually assess the relationship between baseline sweat chloride level and ppFEV1 absolute change from baseline value. For Cohorts 2b-4b, the Day 37 ppFEV1 absolute change from baseline value will be used. For Cohort 6, the Day 43 ppFEV1 absolute change from baseline value will be used. Pearson correlation coefficients may be provided within the plot.

All pulmonary function data obtained from the spirometry assessment will be listed by subject.

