Blood samples will be collected from each subject for metabolic analysis per the SOA. Samples will be frozen at -80°C for analysis outside of this study.

Urine collections will be performed after dosing per the SOA.

Data Analysis:

Healthy volunteers and CF patients will be analyzed separately.

For each healthy volunteers and CF population, subjects will be analyzed by cohorts. Placebo subjects from each cohort will be pooled. In addition, CF patients will also be analyzed in aggregate and separately based on CFTR mutation status and based on use or no use at baseline of a stable regimen (last 2 months) of CFTR modulators/correctors as well as use or no use at baseline of inhaled hypertonic saline.

Screening, Compliance, Tolerability and Safety Data:

In general, safety analyses will be performed based on Safety Analysis Set, which includes all enrolled subjects who receive at least one dose of study drug (placebo or active). Post-dose safety assessments will be compared with measurements recorded at baseline. Treatment-emergent AEs will be summarized using the Medical Dictionary for Regulatory Activities (MedDRA) under version 23.0 or later by System Organ Class (SOC) and Preferred Term (PT). The incidence and frequency of treatment-emergent AEs, SAEs, related AEs, related SAEs, and AEs leading to discontinuation, will be summarized by cohort per SOC, PT, and severity. All AEs, SAEs will also be presented in listings. The duration of AEs will be determined and included in listings, along with the action taken and outcome. The incidence of laboratory abnormalities will be assessed using descriptive summary statistics and shift tables. Vital sign measurements will be summarized at each scheduled time point using descriptive statistics. Abnormal physical examination findings will be summarized by time point and presented in subject listings. ECG parameters, changes from baseline, and qualitative assessments will be summarized. Pregnancy and FSH test results will be listed separately.

Pharmacokinetics:

Plasma concentrations of ARO-ENaC product constituents will be used to calculate the following PK parameters:

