maximum observed plasma concentration (C_{\max}), area under the plasma concentration time curve (AUC) from time 0 to 24 hours (AUC_{0-24}), AUC from time 0 to the last quantifiable plasma concentration (AUC_{last}), AUC from time 0 extrapolated to infinity (AUC_{inf}), and terminal elimination half-life ($t_{1/2}$). Additional PK parameters may be calculated as needed. Pharmacokinetic parameters will be determined using non-compartmental methods. Descriptive statistics of PK parameters will include mean, standard deviation (SD), coefficient of variation, median, minimum, and maximum. PK results will be analyzed for dose proportionality, and sex differences.

PK population: All NHVs and CF patients that received at least one dose of study drug and that have measurable PK concentration data. A subject may be excluded from PK summary and statistical analysis if the subject has a protocol deviation(s) that is thought to impact PK analysis.

NHV Pharmacodynamic (PD) Effect Assessment:

Results, including percent change and duration of response from baseline to EOS will be analyzed and summarized by cohort. The NHV PD population includes subjects in NHV cohort 5.

CF Patient Efficacy Assessments:

Descriptive summary of ppFEV1, LCI, BMI and CFQ-R respiratory domain score at each scheduled study visit and change from baseline will be summarized. Events rate of pulmonary exacerbation will be summarized by cohort.

Immunogenicity (Anti-Drug Antibodies):

Shift tables will be displayed by cohort or by dose in both healthy volunteers and CF patients.

Baseline for data analysis purposes is defined as the pre-dose value occurring closest to the first dose of ARO-ENaC or PBO administered in the study.

Additional details will be provided in the statistical analysis plan.

Table 1.1: Cohorts 1-4:

Assessment	Screen	Day -1 Confine	R	Day 1	Day 2	Day 3	Day 4	Day 5	Day 8	Day 15	Day 29 EOS	Early Term.
Visit Windows	Days -28 to -1			± 5 min for 30 min post dose PK draw and ± 10 min for all other post dose PK timepoints only					± 2 d			
Informed Consent	X											
Eligibility Criteria	X	X										
Body Mass Index/Weight/Height	X			X					X	X	X	X
Demographics	X											
Medical History	X	X										
Drug Screen	X											
Hepatitis/HIV Serology Screen	X											
Physical Exam (may be symptom directed after Day 1)	X			X (pre-dose)	X	X	X	X	X	X	X	X
FSH (in women of post-menopausal age only)	X											
Urine qualitative pregnancy test	X			X (pre-dose)							X	X

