CF Genotyping (See protocol for specifications)	X														
CF Questionnaire			X (pre-dose)					X (pre-dose)			X		X		X
Spirometry	X		X ³	X ³	X ³	X ³	X ³	X ³	X ³	X ³	X ³	X ³	X ³	X ³	X ³
Concomitant Meds/Therapies	X		X	X	X	X	X	X	X	X	X	X	X	X	X

Dose Administration (PBO or Active)			X			X		X								
Urine Cotinine	X															
Anti-drug antibodies			X (pre-dose)			X (pre-dose)		X (pre-dose)								X
Evaluate and Record Occurrence of Pulmonary Exacerbation		X	X	X	X		X	X	X	X	X	X	X	X	X	X
Sweat chloride ⁷			X (pre-dose)													
Adverse Events	X		X	X	X	X	X	X	X	X	X	X	X	X	X	X

1. ECG completed pre-dose (-4hrs ± 30 min) and 2 hours (± 30 min) post-dose on dosing days; any abnormal ECGs will be repeated in triplicate with each measurement approximately 1 minute apart.
2. Plasma PK collected
 - a. Day 1: pre-dose, then based on start of inhalation 30, 60, 120 min, 4 hours, and 24 hours (day 2) post-dose (measured from beginning of drug administration)
 - b. Day 29: pre-dose, then based on start of inhalation 30, 60, 120 min, 4 hours, and 24 hours (day 30) post-dose (measured from beginning of drug administration)
3. Spirometry completed pre-dose and post-dose 60 min (± 20 min), 120 min (± 20 min) on dosing days. Spirometry is only completed once on days when dose is not administered.
4. Order of assessments: 1. Administration of any Standard of Care medications (e.g. hypertonic saline) or airway clearance treatments (e.g. percussion) 2. Lung Clearance Index testing 3. CF Questionnaire, 4. Spirometry evaluation, 5. Draw Blood, 6. Dose administration (on dosing days). Order of other assessments is not protocolized and may be done at discretion of site in concordance with specified ECG/PK windows as well as pre-dose requirements for specified assessments.
5. Chest x-ray to be obtained at days 1, 22, and 113 (or early termination). At all other times, any AE consistent with lower respiratory infection, dyspnea, bronchospasm, or CF exacerbation will trigger a chest X-ray and PFT measurement.
6. At every study visit where LCI is measured per SOA, sites are asked to provide **two** acceptable LCI tests. The final value for data analysis is the mean value of all acceptable washout results.
7. LCI will be measured in all cohort 6 patients, irrespective of ppFEV1. LCI will be performed at all sites when it is available.
7. Sweat chloride to be performed at all sites when available Note: R = randomize.

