- If a subject's Day 1 (pre-dose) baseline spirometry measurement is pre-bronchodilator but the subject fails to withhold bronchodilator on a subsequent visit day, then post-bronchodilator spirometry should be performed on that visit day only
- If a subject fails to withhold bronchodilator on the Day 1 (pre-dose) baseline spirometry measurement, then the Day 1 spirometry measurement should proceed as a post-bronchodilator measurement. Importantly, all subsequent spirometry measurements for that subject should also be performed post-bronchodilator
- Each spirometry assessment will be recorded in the source documents as pre- or post-

bronchodilator

Finally, the above considerations only apply to the initial spirometry assessment of a visit. On dosing days, subjects will also undergo repeat (post-dose) spirometry assessments. Those post-dose spirometry assessments may be either pre-bronchodilator or post-bronchodilator, which should be recorded in the source documents. In CF patients, the initial spirometry assessment of a visit will be used for efficacy assessments, while the post-dose spirometry measures will be used as safety assessments.

- **Cystic Fibrosis Questionnaire-Revised (CFQ-R):** The questionnaire provides information about demographics, quality of life and daily activities. Subjects will be asked to complete the CFQ-R in their native language if valid translations are available. If there is no validated translation then the subject will not complete the questionnaire. Copies of the CFQ-R will be provided in the study Procedural Manual.

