## 5. DEFINITIONS

### Study Day:

Day of study relative to the date of first dose of active drug or placebo. First dose date will be considered as Day 1. Calculated prior to first dose date as (date of measurement – date of first dose) and calculated after first dose date as (date of measurement – date of first dose + 1).

Baseline:

The last observation prior to the first dose of active drug or placebo. The baseline value may be an unscheduled or repeated measurement.

Change (absolute) from baseline:

The arithmetic difference between a post-baseline value and baseline for a given time point: change (absolute) from baseline = (post-dose value – baseline value).

Percent change from baseline:

The percent change between a post-baseline value and baseline for a given time point: [(post-dose value – baseline value) / baseline value] \*100%

Treatment-emergent AEs (TEAEs):

TEAE will be derived as any AEs occurring on or after the first dose.

Treatment-emergent SAEs (TESAEs):

TESAE will be derived as any serious AEs occurring on or after the first dose.

Concomitant Medications:

Concomitant medications will be derived as any medications with an end date on or after the first dose.

Use of medications at baseline:

For each of the following medications: CFTR modulators, inhaled hypertonic saline, inhaled bronchodilators, chronic inhaled antibiotics, inhaled corticosteroids, dornase alfa, and azithromycin, any use within 30 days prior to first dose will be considered as use at baseline. Dornase alfa and azithromycin will be identified by the Preferred Drug Name as coded by WHODrug. All other medications will be identified as recorded on the CF-Concomitant Medications eCRF.

Sputum pseudomonas status at baseline:

Any pseudomonas (as collected on the Airway Infection eCRF) present within 30 days prior to first dose will be considered as positive at baseline.

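### SAP 9.6.1 reports post-dose spirometry only as change from the pre-first-dose baseline, so the same-day acute change at later doses, its spread and the number of subjects with a fall are not reported

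*SAP*

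**What the plan says.** Protocol 10.3.7 splits CF spirometry by purpose. The first test of a visit serves efficacy, "while the post-dose spirometry measures will be used as safety assessments". The schedule supports a same-day comparison. For CF patients, the footnotes to Tables 1.3 and 1.4 read: "Spirometry completed pre-dose and post-dose 60 min (± 20 min), 120 min (± 20 min) on dosing days". For healthy volunteers, the footnotes to Tables 1.1 and 1.2 give a pre-dose test and tests at 15, 60 and 120 minutes on Days 1, 2 and 3.

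SAP section 5 defines a single baseline: "The last observation prior to the first dose of active drug or placebo". The protocol synopsis agrees, defining it as "the pre-dose value occurring closest to the first dose of ARO-ENaC or PBO administered in the study", and says of safety data in general: "Post-dose safety assessments will be compared with measurements recorded at baseline".

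SAP 9.6.1 sets the layout: "Descriptive statistics summaries of pulmonary function parameters obtained from the spirometry assessments will be provided by scheduled timepoint". It then adds: "Absolute changes and percentage changes from baseline will be included". Its bronchodilator sensitivity analysis keeps the same baseline, and individual values are listed. Neither document plans a change from the same-day pre-dose value or a count of subjects with an acute fall.

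**The concern.** For an inhaled product, the acute airway effect of a dose is the post-dose value minus the pre-dose value on that day. On Day 1 the study baseline is in effect that pre-dose value, so the planned summary gives the acute change. At every later dose it does not. The planned figure adds the acute change to any gain, decline or drift since Day 1. A gain makes an acute fall look smaller; a gradual decline can look like an acute reaction.

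If the drug works, the distortion also differs by arm, because active subjects carry a gain that placebo subjects do not. Cohort 6 is where this matters most. It has the highest single-day dose, up to 92.1 mg respirable delivered dose against 30.7 mg in Cohort 4b (Protocol Table 3), and two of its three doses come two and four weeks after baseline. Protocol 5.7 relies on frequent FEV1 measurement to mitigate pulmonary risk.

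**Working it through.** **1. What the 5-point design value is.** Protocol 12.1 and SAP 3.2 size Cohort 6 for a 5-point absolute change in ppFEV1 from baseline at Day 43, with SD 7, significance level 0.05 and power above 80%. Cohort 6 has 18 active and 6 placebo subjects.
- Within-arm test, n = 18: noncentrality = 5 / (7/√18) = 3.03. Two-sided power is 81.5% (t) or 85.8% (normal approximation), which reproduces the stated figure.
- Between-arm test, 18 against 6: two-sided power is 32.8% (normal approximation), which does not.

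The design value is therefore a 5-point gain within the active arm over the study baseline.

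**2. Effect of the reference.** Let g be the gain already present at a later day's pre-dose test and f the true acute fall.
- Change from study baseline = g - f.
- Change from same-day pre-dose = -f.

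The documents give no acute fall and no gain at Days 15, 22 or 29, so g = 0, 2.5 and 5 and f = 3, 5 and 10 are assumptions.

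| True fall f | Same-day reference | Study baseline, g = 0 | g = 2.5 | g = 5 |
|---|---|---|---|---|
| 3 | -3 | -3 | -0.5 | +2 |
| 5 | -5 | -5 | -2.5 | 0 |
| 10 | -10 | -10 | -7.5 | -5 |

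**3. What the planned table still shows.** With g = 5 and f = 5, the pre-dose row reads +5 and the post-dose row reads 0. If the same subjects contribute to both rows, subtracting gives a mean fall of 5. The paired SD, the largest fall and any count of falls cannot be obtained from those rows.

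**4. Precision and counts.** Assume a within-day SD of 3 to 5, a gain SD of 7 (the design SD), independence and n = 18.
- SE of the mean, same-day reference: 3/√18 = 0.7 to 5/√18 = 1.2.
- SE of the mean, study baseline: √(9+49)/√18 = 1.8 to √(25+49)/√18 = 2.0.
- Expected number of the 18 at -10 or below, with mean fall 5 and mean gain 5 (the 10-point cut is only illustrative). For within-day SD 3, 0.9 on the same-day reference against 1.7 on the study baseline. For SD 5, 2.9 against 2.2.

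A count based on the study baseline can therefore err in either direction and is no substitute for a same-day count.

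**5. Where a gain could be present.** Only Cohort 6 is sized on ppFEV1; the other cohorts are sized on the chance of seeing a treatment-emergent adverse event. Days 2 and 3 fall one and two days after baseline. That leaves Days 15 and 29 in Cohort 6 and, if there is benefit by then, Days 22-24 in Cohorts 2b-4b.

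**The case against.** The strongest reply is that nothing is lost. The summary is by scheduled timepoint, while the sensitivity analysis in the same section is by scheduled visit, so separate pre-dose and post-dose rows appear to be intended. Means can be subtracted, pooled placebo is shown beside the active groups, and listings permit recalculation. This stands for the mean. It does not supply the paired spread, the largest fall or the count, and an acute reaction in one or two subjects is an individual event that means conceal.

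A reader might infer several stronger things that the documents do not support.
- That an acute fall is cancelled out of the results. It is offset in one row and remains visible by comparison with the row above.
- That repeat-dose tolerability goes unanswered. Adverse events through end of study are the primary endpoint, bronchospasm or dyspnea events trigger a chest X-ray and pulmonary function test, and confirmed FEV1 drops meeting Protocol 7.4 go to the Data Safety Committee. Symptom reports need not capture asymptomatic falls, however, and the 7.4 criterion is also worded as a drop from baseline.
- That benefit masks falls in healthy volunteers or on Days 2 and 3. No gain is planned or assumed there; at most there is short-term drift.
- That the SAP departs from the protocol. It follows the protocol's own baseline and comparison for safety data.

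The same-day change also has limits. Each pre-dose value resets the reference, so it cannot show cumulative decline. Post-dose tests may be taken with or without a recent bronchodilator (Protocol 10.3.7), which can itself hide or distort an acute fall.

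**Conclusion.** The point holds as a gap in reporting. After the first dose, the only planned change statistic combines the acute effect with change since Day 1, and the distribution of the acute change and the number of subjects with a fall are not produced.

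The size is conditional. A 5-point fall would read between -5 and 0 if the pre-dose gain lay between 0 and 5 points. The upper value is a Day 43 design figure for Cohort 6, so full offset on Day 15 or Day 29 is an assumption, and Cohorts 2b-4b have no sized effect at all. The precision figures rest on assumed within-day SDs and independence.

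The data needed for the paired change are already scheduled, and the primary endpoint is not affected. This is a worthwhile, low-cost addition to a descriptive analysis.

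**What to change.** In SAP 9.6.1, add a safety table for each population giving the change in FEV1 and ppFEV1 from the same-day pre-dose value to each post-dose timepoint. Present it by dosing day and treatment group, with pooled placebo shown. Include the paired mean, SD, minimum and maximum, and the number of subjects exceeding falls that the sponsor states in advance. Identify bronchodilator status at both the pre-dose and post-dose test. SAP 9.6.1 already takes this from the eCRF for CF patients; for healthy volunteers the protocol places it in source documents, so the SAP should say whether it is available for analysis.

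Add this alongside the change from study baseline, not in its place. The study-baseline change is still needed for the healthy-volunteer secondary FEV1 endpoint (Protocol 6.2), for cumulative safety across doses and for CF efficacy.

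The cost is one extra table per population, with no additional spirometry and no change to trial conduct.

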ECG ⁴	X	X		X	X	X	X	X	X	X	X	X
Vital Signs (BP, temp, pulse ox., RR, heart rate) perform before other evaluations	X	X		X	X	X	X	X	X	X	X	X
Clinical Labs (heme, coag, chem, UA, Urine electrolytes)	X	X		X (pre-dose)	X (pre-dose)	X (pre-dose)	X		X	X	X	X
PK ²				X	X	X	X	X				
Plasma metabolite ID				X	X	X	X		X	X		
Urine collection for excretion and metabolite ID ³						X	X					
Chest X-ray (PA and Lateral) ⁵	X									X	X	X
Spirometry ¹	X	X							X	X	X	X
Concomitant Meds/Therapies	X	X							X	X	X	X
Adverse Events	X	X							X	X	X	X
Dose Administration (PBO or Active)												
Urine Cotinine	X											
Anti-drug antibodies		X									X	

1. On dosing days (Days 1,2,3), completed at immediate pre-dose, 15 min (± 10 min), 60 min (± 10 min), 120 min (± 10 min). On non-dosing days, only completed once per visit.
2. Plasma PK collected:
 - a. Day 1: Pre-dose, then based on start of inhalation 30, 60, 120 min, 4, 6, 8, 16 hours.
 - b. Day 2: Pre-dose (Day 1, 24 hr timepoint), then based on start of inhalation, 1, 2, 4 hours
 - c. Day 3: Pre-dose (Day 2, 24 hr timepoint), then based on start of inhalation, 30, 60, 120 min, 4, 6, 8, 16, 24 (on Day 4), 48 hours (on Day 5).
3. Urine collected cumulatively from 0-6 hours and 6-24 hours post dose on Day 3 through Day 4. Subject should void pre-dose on Day 3. Metabolite ID will be performed on urine samples collected (pooled analysis).
4. On dosing days, ECG performed pre-dose (-4hrs) and 2 hours (± 10 min) post-dose; any abnormal ECG's will be repeated in triplicate with each measurement approximately 1 minute apart.
5. Chest x-ray to be performed at screening, day 15, and day 29 (or early termination). At all other times, any AE consistent with lower respiratory infection, dyspnea, or bronchospasm will trigger a chest X-ray and PFT measurement.

Note: R = randomize.

Table 1.2: Cohort 5:

Assessment	Screen	Day 0 Confine	R	Day 1	Day 2	Day 3	Day 4	Day 5	Day 8	Day 18	Day 19	Day 29 EOS	Early Term.
Visit Windows	Days -28 to -1			± 5 min for 30 min post dose PK draw and ± 10 min for all other post dose PK timepoints only					± 2 d	± 3 d	+ 2d	± 2 d	
Informed Consent	X												
Eligibility Criteria	X												
Body Mass Index/Weight/Height	X			X					X	X		X	X
Demographics	X												
Medical History	X												
Drug Screen	X												
Hepatitis/HIV Serology Screen	X												
Physical Exam (may be symptom directed after Day 1)	X	X		X (pre-dose)	X	X	X	X	X	X		X	X
FSH (in women of post-menopausal age only)	X												

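### CF post-dose safety spirometry is summarised with rules suited to the efficacy test, so a fall treated with a bronchodilator before the 60-minute test can be reduced or absent in the means of both planned summaries

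*SAP*

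**What the plan says.** Protocol 10.3.7 divides CF spirometry into two series. The first test of a visit serves efficacy and should be pre-bronchodilator. The withholding rules stop there. Of the later tests on dosing days the protocol says: "Those post-dose spirometry assessments may be either pre-bronchodilator or post-bronchodilator, which should be recorded in the source documents". Their purpose in CF patients is also stated: "while the post-dose spirometry measures will be used as safety assessments". Protocol 10.7 lists spirometry among the safety measurements.

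The schedule notes to Tables 1.3 and 1.4 of the protocol synopsis set the CF times: "Spirometry completed pre-dose and post-dose 60 min (± 20 min), 120 min (± 20 min) on dosing days". Healthy volunteers have an additional test at 15 minutes (Tables 1.1 and 1.2).

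SAP 9.6.1 acknowledges that CF spirometry is both a safety and an efficacy measurement, but has one set of rules for it:

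- Main summary: "Descriptive statistics summaries of pulmonary function parameters obtained from the spirometry assessments will be provided by scheduled timepoint", with absolute and percent change from baseline. SAP section 5 defines baseline as the last value before the first dose of the study.
- Flag: "All CF patient spirometry summaries will identify use of an inhaled bronchodilator as recorded on the Spirometry eCRF". How this will be shown is not described.
- Sensitivity analysis of FEV1 and ppFEV1, run if any CF patient has a mismatch: "excluding any post-baseline spirometry assessments where the bronchodilator status does not match the bronchodilator status at baseline".

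SAP 9.5 (Safety Analyses) has no spirometry subsection. Neither 9.5 nor 9.6.1 plans a lowest post-dose value, a count of falls, a change from the same day's pre-dose test, or a count of bronchodilator use around dosing.

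**The concern.** At the first test of a visit, a bronchodilator mismatch means that a patient did not withhold. That is a nuisance unrelated to the acute effect of the dose, and dropping the value in a sensitivity analysis is sensible.

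At a post-dose test, the bronchodilator may have been taken because FEV1 fell after the inhalation. Keeping the value then records the treated level, and dropping it removes the subject because of the outcome under study. The two analyses may agree with each other while neither mean shows the fall.

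What is at stake is whether the post-dose FEV1 series can do its stated safety job for an inhaled product. The protocol relies on frequent FEV1 measurement to mitigate pulmonary risk (5.7). The CF cohorts have no test before 60 minutes, and Cohort 6 has the largest loaded dose and the longest nebulization time (Table 3).

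**Working it through.** The documents give no figure on this point, so there is none to reproduce. The check follows a treated post-dose value through the rules and then does the arithmetic on assumed inputs.

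**Tracing one value.** Take a patient with a pre-bronchodilator baseline whose FEV1 falls after dosing.

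1. Bronchodilator taken before the 60-minute test: the main summary holds the treated value; the sensitivity analysis, read literally, drops it as a mismatch.
2. Bronchodilator taken only after the 60-minute test: the fall is in the 60-minute main summary and stays in the sensitivity analysis. Only the 120-minute value is affected.
3. Baseline was post-bronchodilator: Protocol 10.3.7 then says "Importantly, all subsequent spirometry measurements for that subject should also be performed post-bronchodilator". A treated value matches baseline and is not dropped.

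Only route 1 can affect the means of both summaries at 60 minutes.

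**Inputs.** From the documents: n = 18 active in Cohort 6 and n = 9 active in Cohort 4b (protocol Table 4). Assumed: k subjects fall F points of ppFEV1, a bronchodilator taken before the test restores a fraction r, all other subjects change by 0, and baseline is pre-bronchodilator.

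**Formulas.**
- Mean change before treatment = −F·k/n
- Main summary = −F·(1−r)·k/n
- Sensitivity analysis = mean of the remaining n−k subjects = 0

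**Cohort 6, F = 15, n = 18.**

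| k | Before treatment | Main, r = 1 | Main, r = 0.5 | Sensitivity |
|---|---|---|---|---|
| 1 | −15·1/18 = −0.83 | 0 | −0.42 | 0 on 17 subjects |
| 2 | −15·2/18 = −1.67 | 0 | −0.83 | 0 on 16 subjects |
| 3 | −15·3/18 = −2.50 | 0 | −1.25 | 0 on 15 subjects |

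**Range.** With F = 20, the means before treatment for k = 1, 2, 3 are −1.1, −2.2 and −3.3 in Cohort 6, and −2.2, −4.4 and −6.7 in Cohort 4b (n = 9). Half restoration again leaves half of each in the main summary.

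**Direction between arms.** The rules apply equally to placebo, which is pooled across CF cohorts: 2 + 2 + 3 + 6 = 13 planned. Suppose one Cohort 6 active subject and one placebo subject each fall 15 points on Day 1 and are fully restored. The hidden falls are 15/18 = 0.83 (active) and 15/13 = 1.15 (placebo). Both arms show 0, although before treatment the active mean was the better one by 0.32. The bias can therefore run against active as well as for it.

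**The case against.** Four objections have weight.

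*The exclusion may not be meant for post-dose tests.* The main summary is by scheduled timepoint and the sensitivity summary is by scheduled visit. It sits under Efficacy Analyses, and the LCI section (9.6.2) has parallel text although LCI has no post-dose series. A narrower reading is reasonable. But the wording covers any post-baseline assessment, and under the narrow reading the post-dose safety values have no bronchodilator handling beyond the flag. Either reading calls for an edit.

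*Other routes capture a reaction.* A reader might infer that an acute airway reaction vanishes from the trial's results. The documents do not support that. Adverse events are the primary endpoint and are tabulated by severity and relationship (SAP 9.5.1). An event of bronchospasm or dyspnea triggers a chest X-ray and lung function test. Every spirometry value is listed, concomitant medications are summarised, and a confirmed fall of at least 20 points judged probably related goes to the Data Safety Committee (Protocol 7.4). CF FEV1 is exploratory and no hypothesis is tested. These routes stand, with limits: listings give no comparison by arm, and the medication summary counts subjects per drug with no link to dosing, so a habitual bronchodilator user is counted regardless.

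*The rules cannot only favour active.* A reader might infer that they do. They apply to both arms and placebo is also nebulised, so the direction depends on which arm has more treated reactions.

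*Most bronchodilator use may be routine.* CF patients keep their regimen and need withhold only before the first test. Use after that test is foreseeable and need not signal a reaction. This stands, and it rules out a composite event that counts all such use.

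**Conclusion.** The concern holds in a limited form. The SAP does not carry over the protocol's division between the efficacy test and the post-dose safety tests. As a result, a fall treated before the 60-minute test can be reduced or absent in the means of both the main and the sensitivity summary.

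The size cannot be known from the documents. Under the assumptions shown, the hidden mean fall in Cohort 6 is 0.8 to 2.5 points for 1 to 3 subjects falling 15 points. That requires a pre-bronchodilator baseline, use before the test and full restoration. Half restoration halves it in the main summary. Total masking is the extreme case.

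The primary endpoint is not affected. The weakness lies in the post-dose FEV1 tables, and it merits a SAP correction before Cohort 6 is unblinded.

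**What to change.** 1. In SAP 9.6.1, state that the bronchodilator-mismatch exclusion applies only to the initial spirometry of each visit.

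2. Add one CF safety table of post-dose spirometry, by treatment group, dosing day and timepoint, showing:
   - change in ppFEV1 from the same day's pre-dose test;
   - number and percent of subjects with falls of sizes fixed before unblinding;
   - as a separate row, number and percent whose recorded bronchodilator status changed from that day's pre-dose test. These subjects are counted and kept in.

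The same-day comparison also helps on Days 15 and 29 of Cohort 6, where change from the Day 1 baseline mixes the acute effect with drift between visits. Bronchodilator use should not be merged with FEV1 falls into one event.

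The cost is a wording change and one more table, built from values and bronchodilator status that SAP 9.6.1 says are recorded at each CF test. Patient care does not change.

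The limitation is that the status row cannot separate routine from reaction-driven use. It also cannot separate use before dosing from use after it, because the initial spirometry precedes the blood draw and the dose, and the protocol specifies medication dates but not clock times (10.3.10). Nor can it show further use by a subject already post-bronchodilator that day. It should be labelled descriptive unless times of use are recorded.
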